Within the treatment cohort, blinded treatment with the investigational drug (VAY736 or CFZ533) or placebo will be administered on top of patients' stable standard of care therapy for SLE. Visits to assess safety and/or efficacy are scheduled at 4-week intervals. An additional safety visit is scheduled at Week 3 (within the placebo-controlled period) and Week 31 (within the open label period) where patients in Cohort 2 (CFZ533) will receive an additional treatment dose (see [Section 4.2.2](#)).

At the baseline visit Day 1, following patient eligibility confirmation and completion of all assessments, first dose of study drug/placebo will be administered. The last treatment in the blinded treatment period will be given at the Week 25 visit. The readout for the blinded treatment period will be performed at Week 29. Study drug will be administered every 4 weeks. Unless otherwise stated, all assessments must be completed BEFORE the next dose of study drug is administered.

Guided corticosteroid (CS) reduction

- Patients entering the study on a stable CS regimen are required to undergo a guided CS taper from baseline levels starting at Week 5 in order to achieve by Week 17:
 - a daily CS dose of ≤ 5 mg/day prednisone or equivalent,
 - or a CS dose that is less than the baseline dose, whichever is the lower dose.
- In addition, the patient should remain at the lowered CS dose achieved at Week 17 through to Week 29.
- Patients entering the study without background CS therapy should remain free of any CS regimen or increase in SoC DMARDs through to Week 29.
- Patients exceeding the rescue therapy allowances may continue in trial but will be labeled a non-responder for primary endpoint.
- During the open label phase, further reductions in patients' SoC CS and DMARDs may be made on an individual basis as deemed appropriate by the investigator. For details on the guided CS tapering please refer to [Section 6.2.2](#)

Open-label treatment phase

At the end of the Week 29 visit, after all assessments have been performed, the first -open label treatment will be administered. Patients in Cohort 1 will receive VAY736 and patients in Cohort 2 will receive CFZ533. Study drug will be administered every 4 weeks. The last treatment will be given at the Week 49 visit, and the End-of-Treatment (EoT) visit will be performed 4 weeks thereafter, at Week 53.

Follow-Up period

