4.5.4 Blood sample volume

A total blood volume of approximately 790 mL will be collected over the course of the initial 13-month screening / treatment phase up to Study Week 53. Approximately 205 mL of additional blood will be collected during the 4-month Follow-up period (Study Week 57 to Week 69). Thus, for the entire study from Screening until the Week 69 visit, an overall total blood volume of approximately 995 mL over 18 months will be collected.

For patients tested positive for HepBc Ab, an additional overall blood volume of approximately 140 mL will be taken up to V399 (Month 18) for both Cohorts. Monthly hepatitis B monitoring will be continued after V399 to V400 (12 months after last treatment) for all patients in Cohort 1 who tested positive for HepBc Ab. For patients who do not achieve B cell recovery, testing will continue at every visit (8 mL at each visit) until EoS visit Cohort 1.

For patients randomized to the CFZ533 cohort, an additional blood volume of approximately 115 mL from Baseline until Week 69 will be collected for local CMV monitoring.

Patients in Cohort 1 (VAY736) who do not achieve B cell recovery criteria at the Week 69 visit will continue the study and enter into a secondary Follow-Up period starting after the Week 69 visit has been completed. At each of the visits in the secondary Follow-Up period, approximately 15 mL of blood (plus 8 mL if HepB monitoring is required) will be collected to monitor safety laboratory and B cell recovery. At EoS visit for Cohort 1 approximately 60 mL of blood will be collected. Since each patient in Cohort 1 (VAY736) will have an individual follow-up time to achieve B cell recovery criteria, a total blood volume taken throughout the study cannot be given. Additional samples may be required for safety monitoring or repeat measures.

Timings of blood sample collection are outlined in the [Assessment Schedule](#).

A summary blood log is provided in the Site Operations Manual (SOM). Instructions for all sample collection, processing, storage and shipment information is also available in the SOM and central laboratory manual.

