6.2.3 Prohibited medication

Use of the treatments displayed in the below [Table 6-3](#) are not allowed after the start of the study.

Table 6-3 Prohibited medication

Medication	Prohibition period	Action taken
Other immune suppressive agents and biologics: 
 • Calcineurin inhibitors • Cyclophosphamide, intravenous Ig, plasmapheresis, anti-TNF-α mAb, CTLA4-Fc Ig (abatacept) or BAFF targeting agents (e.g., belimumab) • Any B cell depleting therapies (e.g., anti-CD20 mAb, anti-CD22 mAb, anti-CD52 mAb), atacicept, (TACI-Ig) 	Throughout treatment period through EoS	Withdrawal may be required on a case-by-case basis
• Total CS >30 mg/d prednisone or equivalent	Throughout treatment period through Week 29	Designated non-responder for primary endpoint
• Changes in CS dose	Within 2 weeks of Study Visit Week 29	Designated non-responder for primary endpoint
• Other experimental therapies	Throughout treatment period through to EoS	Withdrawal may be required on a case-by-case basis
• Live/ attenuated vaccines	
 • For Cohort 1 (VAY736): Throughout treatment period and follow up period up to 2 years after the EoT or until achieving B cell recovery (whichever occurs earlier) • For Cohort 2 (CFZ533): Throughout treatment period and up to 14 weeks after last CFZ533 dosing 	Study treatment discontinuation; patient should remain in study and follow visit schedule for safety monitoring until achieving EoS visit for their respective cohorts

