² Cohort 1 (VAY736), only: End of study visit will be performed as soon as practically possible but no more than approximately 4 weeks after this clinical protocol amendment is approved, independently of B cell recovery criteria reached as long as visit occurs 2 years after EoT. If a patient's B cell recovery is confirmed at Week 69, no additional follow-up or EoS visit is needed, and therefore Week 69, FU 1 Cohort 1/ EoS Cohort 2 will be the last visit.

³ Cohort 1 (VAY736), only: Follow-up visits in Cohort 1 have to be performed up to 2 years after EoT or until B cell count is at ≥ 50 cells/ul or at least 80% of baseline levels, whichever occurs earlier. If a patient B cells recovery is confirmed at Week 69 no additional follow-up or EOS visit is needed, and therefore Week 69, FU 1 Cohort 1/ EoS Cohort 2 will be the last visit.

⁴ Body Weight, Temperature, Blood Pressure, Pulse Rate

⁵ Pregnancy test on Visit 1 (Screening) in serum, all other visits in urine, only women

CCI

⁷ Central Lab

CCI

¹⁵ Monthly HepB monitoring will be continued after V399 to V400 for all patients in Cohort 1 who tested positive for HepB core Ab. For patients who do not achieve B cell recovery, testing will continue at every visit until EoS visit Cohort 1.

¹⁶ This test will only be applied for HepBc Ab positive patients at screening; followed by monthly HBV DNA and HBsAg testing.

¹⁷ CMV test (CMV serologies IgG and IgM and CMV DNA by PCR) will be continued at the local laboratory after V300 to V399 on a monthly basis only for patients randomized to Cohort 2 (CFZ533)

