 - CMV monitoring is increased to at least weekly intervals of DNA monitoring by serial PCR assessments as well as clinical monitoring for early signs of CMV end organ disease until resolution
 - consider initiation of pre-emptive anti-CMV therapy when PCR-determined viral load is $>1,000$ copies/mL, in consultation with an infectious disease expert
 - consider reducing or stopping the dose of other immunosuppressive agents
 - consider stopping the study drug
 - if primary CMV infection is suspected, based on confirmed prior negative serology CMV IgG, repeat CMV IgG serology after resolution of primary infection and after completion of study treatment
- During the study, for patients with confirmed or probable CMV disease activity who develop clinical symptoms, it is required that:
 - appropriate anti-CMV therapy is initiated
 - the study drug is stopped
 - consider stopping or reducing the dose of other immunosuppressive agents

For patients with potential infectious symptoms during the trial in the absence of laboratory support of CMV etiology, consider age- and country-appropriate infectious exposure risks; consider direct isolation of pathogens, virology, and/or serology and initiating appropriate targeted anti-viral or anti-bacterial therapies as indicated in consult with an expert.

Guidance to investigators

CMV infections will be recorded as Adverse Events and on the CMV-specific CRF. CMV infection is identified by assessments of laboratory and/or clinical signs/symptoms ([Ljungman et al 2017](#)).

- Laboratory-defined CMV (antigenemia-positive, PCR positive).
- CMV syndrome (fever for 2 days, neutropenia, leucopenia, viral syndrome)
- CMV disease (organ involvement).

Infections

All occurrences of infections must be carefully monitored by the Investigator.

Significant findings meeting the definition of infection must be recorded in the Adverse Event eCRF.

IMI samples

Novartis is a member of a consortium of the European Innovative Medicines Initiative (IMI). Novartis will contribute blood and urine samples from placebo-treated patients enrolled in this SLE study from selected sites to the IMI biobank for additional research within this IMI project.

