9.1 Discontinuation

9.1.1 Discontinuation of study treatment

Discontinuation of study treatment for a subject occurs when study treatment is stopped earlier than the protocol planned duration and can be initiated by either the subject or the investigator. The investigator must discontinue study treatment for a given patient if, on balance, he/she believes that continuation would negatively impact the risk/benefit of trial participation.

Study treatment must be discontinued under the following circumstances:

- Subject/guardian decision - subjects may choose to discontinue study treatment for any reason at any time
- The investigator believes that continuation would negatively impact the safety of the subject or the risk/benefit ratio of trial participation
- Severe injection-related reactions (Cohort 1, VAY736) or infusion-related reactions (Cohort 2, CFZ533). Immediate interruption of the study drug administration is required where possible in such cases
- Severe hypersensitivity reaction e.g., anaphylaxis. Immediate interruption of the infusion/injection is required in such cases.
- Pregnancy (see [Section 10.1.4](#) (Pregnancy reporting))
- Patient received a live/ attenuated vaccine
- Reactivation of hepatitis B infection (e.g., seroconversion of HBsAg or detection of viral DNA); suspected or confirmed active CMV infection (see [Section 8.4.4](#), Hepatitis, HIV and CMV screening)
- Any situation or protocol deviation that may result in a significant safety risk to the patient
- Patient withdraws his/her consent (when patients also must be withdrawn from the study)
- Adverse events, abnormal laboratory values or abnormal test results that indicate a safety risk to the patient.
- Use of prohibited treatment as outlined in [Table 6-3](#)
- In addition, in case of emergence of the following adverse events, discontinuation must be considered jointly by the investigator and Novartis:
 - Persistent neutropenia $\leq 1,000/\mu\text{l}$ that may preclude further administration of a B cell depleting agent (Cohort 1, only: VAY736/Placebo)
 - Cohort 2 (CFZ533/Placebo) only: significant changes in standard coagulation parameters, including prothrombin time (PT) and activated partial prothrombin time (aPTT) suggesting an increased risk for hypercoagulability or any sign or symptom of a thromboembolic event
 - SAEs or severe AEs of infection that are suspected to be related to study treatment

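### Protocol 9.1.1 orders treatment stops that Table 6-3 and the CMV guidance do not, and hepatitis B monitoring has two end points for Cohort 1 patients whose B cells recover by Week 69

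*Protocol*

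**What the plan says.** **Prohibited medication.** The list in Protocol 9.1.1 opens with "Study treatment must be discontinued under the following circumstances", and one entry is "Use of prohibited treatment as outlined in" Table 6-3. In that table (Protocol 6.2.3), the action for each of the two corticosteroid (CS) rows is "Designated non-responder for primary endpoint". The rows for immunosuppressants/biologics and for experimental therapies say that withdrawal may be needed, judged case by case. Only the live/attenuated vaccine row names discontinuation of study treatment. Protocol 3, under guided corticosteroid reduction, says "Patients exceeding the rescue therapy allowances may continue in trial but will be labeled a non-responder for primary endpoint".

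**CMV.** The same 9.1.1 list includes "suspected or confirmed active CMV infection", with a cross-reference to 8.4.4. For asymptomatic active infection, defined there by quantifiable CMV DNA, 8.4.4 says "consider stopping the study drug". It requires a stop for confirmed or probable disease with symptoms.

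**Hepatitis B, Cohort 1.** Protocol 4.5.4 says "Monthly hepatitis B monitoring will be continued after V399 to V400 (12 months after last treatment) for all patients in Cohort 1" who are core-antibody positive. Table 8-2 footnote 15 repeats the V400 rule without the 12-month label. Both extend testing to end of study (EoS) for patients without B cell recovery. Section 8.4.4 sets monitoring at study visits until EoS, and anti-viral prophylaxis until 12 months after last treatment. Table 8-2 footnote 3 says "If a patient B cells recovery is confirmed at Week 69 no additional follow-up or EOS visit is needed", and footnote 2 says the same.

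**The concern.** Two sites following different sections could stop or continue drug in the same situation. A patient kept on drug would then comply with one passage and deviate from another. Whether dosing continues affects exposure, PK, flare, the physician's and patient's global assessments, and entry to open-label treatment.

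The CMV conflict has one further consequence. SAP 7.1.1 counts drop-out before Week 29 as non-response but does not mention a treatment stop on its own, so a patient stopped for CMV who stays in the study has no explicit responder rule.

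For hepatitis B, a recovered core-antibody-positive patient could be released from visits at Week 69 under one set of footnotes, while another passage still calls for monthly tests and 8.4.4 still calls for prophylaxis.

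**Working it through.** **1. Section 9.1.1 against Table 6-3, row by row**

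| Table 6-3 row | Table 6-3 action | 9.1.1 | Agree? |
|---|---|---|---|
| Immunosuppressants/biologics | Case-by-case withdrawal | Stop | Unclear |
| Total CS above 30 mg/d | Non-responder | Stop | No |
| CS change within 2 weeks of Week 29 | Non-responder | Stop | No |
| Experimental therapies | Case-by-case withdrawal | Stop | Unclear |
| Live/attenuated vaccines | Treatment discontinuation | Stop | Yes |

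The two unclear rows depend on whether withdrawal means leaving the study or stopping drug.

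Effect on the primary endpoint: Table 6-3, Protocol 6.2.4 and SAP 7.1.1 make excess CS a non-response whether or not dosing continues. SAP 7.1.1 also counts use of other Table 6-3 medication as non-response.

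Effect on blinded exposure: the last blinded dose is at Week 25 (Day 169). Two weeks before Week 29 (Day 197) is Day 197 − 14 = Day 183, which is after that dose. A stop triggered by the CS-change row before the Week 29 visit therefore cannot alter blinded dosing or the Week 29 assessments. It can only bar open-label dosing. A stop triggered by the 30 mg/d row can affect both periods.

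**2. CMV**

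| Situation | 9.1.1 | 8.4.4 | Agree? |
|---|---|---|---|
| Confirmed or probable disease with symptoms | Stop | Stop | Yes |
| Asymptomatic active infection | Stop | Consider stopping | No |
| Suspected active infection | Stop | No mandatory stop unless symptomatic and at least probable | No |

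Table 8-1 footnote 25 limits routine CMV testing after screening to Cohort 2, so the conflict arises mainly there.

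**3. Hepatitis B monitoring**

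Inputs: last dose at Week 49, Day 337 ±4 (Table 8-1); EoT Day 365 (Table 8-1); V399 at Week 69, Day 477 (Table 8-2); V400 at Week 93, Day 645 ±10 (Table 8-2). One month = 365.25/12 = 30.44 days.

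Reproducing the 12-month label for V400:
- From last dose: 645 − 337 = 308 days; 308/7 = 44 weeks; 308/30.44 = 10.1 months.
- Window extremes: (645 − 10) − (337 + 4) = 294 days, and (645 + 10) − (337 − 4) = 322 days, or 9.7 to 10.6 months.
- In 28-day months: 308/28 = 11.0.
- By the tables' own month rows: 24 − 13 = 11.
- From EoT: 645 − 365 = 280 days, or 9.2 months.

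None gives 12. Twelve months after the last dose is 337 + 365 = Day 702, about Week 101. That is 702 − 645 = 57 days, about 8 weeks, after V400.

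End points for a core-antibody-positive Cohort 1 patient:
- Recovered at Week 69: last visit Day 477 by footnotes 2 and 3, against V400 (Day 645) by 4.5.4 and footnote 15. Day 477 is 477 − 337 = 140 days (20 weeks) after the last dose and 702 − 477 = 225 days (about 32 weeks) before 12 months.
- Not recovered: 4.5.4, footnote 15 and 8.4.4 all give EoS, so there is no conflict.

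Table 8-2 schedules no visit between Week 69 and Week 93, so the monthly tests in footnote 15 have no visits to attach to.

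**The case against.** The strongest defence of 9.1.1 is that its reference to Table 6-3 imports that table's action column. The entry would then be nearly empty, because the only row ordering a stop is live vaccines, which already has its own entry in 9.1.1. The table also names treatment discontinuation where it means it.

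Part of the defence stands. Section 9.1.1 itself separates stopping treatment from leaving the study. Case-by-case withdrawal may mean study withdrawal, which is compatible with a mandatory drug stop. Remaining in the trial (Protocol 3 and 4.1) does not strictly mean remaining on drug. The clearest tension is therefore in the two CS rows. In addition, the rescue criterion of more than 2 days of increased dose per cycle (6.2.4) is not a Table 6-3 row and does not trigger the 9.1.1 entry.

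On hepatitis B, footnote 15 is the specific rule and already runs outside the visit grid, so the release of recovered patients need not cancel it. Some text near exclusion criterion 15 and some Table 8-2 footnotes are redacted, so an exception could exist there.

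Stronger readings may suggest themselves, but the documents do not support them:
- That unequal CS use biases the primary comparison. The documents give no rate at which either arm exceeds the limits, and responder status is the same under both readings.
- That the 20% to 80% core-antibody prevalence in Protocol 4.1 is the share affected. It describes adult and target populations in Asia-Pacific countries. The affected group is only enrolled, positive, Cohort 1 patients recovered at Week 69, and no count is given.
- That hepatitis B monitoring is contradictory for all of Cohort 1. For non-recovered patients the passages agree.

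**Conclusion.** The passages conflict, within narrow limits. Section 9.1.1 clearly disagrees with Table 6-3 for the two CS rows, is ambiguous for two others, and agrees for vaccines. Sections 9.1.1 and 8.4.4 disagree for suspected or asymptomatic active CMV infection only. For recovered core-antibody-positive Cohort 1 patients, hepatitis B monitoring ends at Week 69 or at Week 93, and the 12-month label on V400 is about 8 weeks out. The date results rest on the nominal schedule, and the visit windows do not close the gap.

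Primary-endpoint status for the CS rows is unaffected. What is affected is whether dosing continues, and through it exposure, secondary endpoints and open-label entry. The number of patients cannot be derived from the documents.

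Prospective effect is limited. SAP 5 states that final Cohort 2 results have been reported, and SAP 1.4 applies the amendment 5 follow-up rule only to the last 3 patients. The remaining value is mainly in classifying deviations and in reporting which rule was applied.

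**What to change.** The sponsor should reconcile three sets of passages so that each situation has one rule:
- 9.1.1 with Table 6-3, stating for each row whether study treatment, study participation or only responder status is affected;
- 9.1.1 with 8.4.4 on suspected and asymptomatic active CMV infection;
- 4.5.4, 8.4.4 and Table 8-2 footnotes 2, 3 and 15 on when hepatitis B monitoring ends for recovered and non-recovered Cohort 1 patients, with a V400 label that matches the scheduled day.

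Which rule should prevail is for the sponsor to decide. The clinical study report should state which rule was applied during the trial and how departures were classified. The cost is a clarification letter or short amendment and a paragraph in the report. Any extra hepatitis B testing would depend on the end time confirmed and would concern only patients still in follow-up.

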9.1.2 Replacement policy

Over-recruitment of approximately 10% will be allowed to compensate for early dropouts.

9.1.3 Withdrawal of informed consent

Subjects may voluntarily withdraw consent to participate in the study for any reason at any time. Withdrawal of consent occurs only when a subject:

- Does not want to participate in the study anymore, and
- Does not allow further collection of personal data

In this situation, the investigator should make a reasonable effort (e.g., telephone, e-mail, letter) to understand the primary reason for the subject's decision to withdraw his/her consent and record this information.

Study treatment must be discontinued and no further assessments conducted, and the data that would have been collected at subsequent visits will be considered missing.

Further attempts to contact the subject are not allowed unless safety findings require communication or follow-up.

All efforts should be made to complete the assessments prior to study withdrawal. A final evaluation at the time of the subject's study withdrawal should be made as detailed in the [assessment table](#).

Novartis will continue to keep, and use collected study information (including any data resulting from the analysis of a subject's samples until their time of withdrawal) according to applicable law.

For Japan and US: all biological samples not yet analyzed at the time of withdrawal may still be used for further testing/analysis in accordance with the terms of this protocol and of the informed consent form.

For EU and RoW: all biological samples not yet analyzed at the time of withdrawal will no longer be used, unless permitted by applicable law. They will be stored according to applicable legal requirements.

9.1.4 Lost to follow-up

For subjects whose status is unclear because they fail to appear for study visits without stating an intention to discontinue or withdraw, the investigator must show "due diligence" by documenting in the source documents steps taken to contact the subject, e.g., dates of telephone calls, registered letters, etc. A subject should not be considered as lost to follow-up until due diligence has been completed.

9.1.5 Study/ Cohort stopping rules

The relevant study cohort will be put on hold for further enrollment pending further safety data analysis if any of the following criteria occur in patients receiving VAY736 or CFZ533:

- Any death or life-threatening event suspected to be related to study treatment
- Persisting changes from baseline in vital signs, electrocardiograms of potentially life-threatening severity, or relevant, persistent changes in laboratory parameters which are not consistent with existing co-morbidities or the desired experimental compound mechanism-of-action (e.g., B cell depletion by VAY736), in >1 patient within the first 5 treated subjects or an incidence of >20% thereafter
- Three (3) or more patients per cohort with a similar adverse event of severe intensity with the following exceptions:
 - Events of Special Interest, including injection-related (hypersensitivity, cytokine release), decreased neutrophil or leukocyte counts not requiring treatment, and diagnostic procedures involving elective or non-urgent hospital admission
 - Disease-Specific Events that are due to the patient's underlying SLE diagnosis
 - AEs/SAEs clearly unrelated to the experimental compound as determined by the investigator or Novartis
- Two (2) or more patients per cohort presenting with active treatment-suspected toxicities, including:
 - Severe systemic infection or severe opportunistic infection that requires treatment, e.g., sepsis, urosepsis, mycoses, pneumonia
- *Cohort 1, VAY736 treatment arm only*: more than one (1) injection-related reaction of severe intensity within the first five (5) treated patients or an incidence of >20% thereafter
- *Cohort 2, CFZ533 treatment arm only*: one (1) patient presenting with suspected CFZ533-related thromboembolic event that is at least of moderate severity and is unrelated to pre-existing co-morbidities

The investigator must also contact the IRT to register the patient's discontinuation from study treatment and/or from study.

If discontinuation occurs because the treatment code has been broken, please refer to Emergency breaking of treatment code section.

The study may resume following the safety review, if the Investigators and Sponsor agree it is safe to proceed.

